### **6.1.2 DOSING AND ADMINISTRATION**

Dosing is not applicable to this trial involving the investigation of a medical device, as opposed to a medication. Administration is described above in 6.1.1.

## **6.2 PREPARATION/HANDLING/STORAGE/ACCOUNTABILITY**

---

### **6.2.1 ACQUISITION AND ACCOUNTABILITY**

The machines and the probes for cryoneurolysis will be stored in a locked office or workroom.

---

### **6.2.2 FORMULATION, APPEARANCE, PACKAGING, AND LABELING.**

Not applicable to this trial involving the investigation of a medical device, as opposed to a medication.

---

### **6.2.3 PRODUCT STORAGE AND STABILITY**

The machines and the probes for cryoneurolysis will be stored in a locked office or workroom.

---

### **6.2.4 PREPARATION**

Sterile probes will be used for the study intervention—they do not need “preparation”.

## **6.3 MEASURES TO MINIMIZE BIAS: RANDOMIZATION AND BLINDING**

These protocols will use a randomized, observer- and participant-masked, sham/placebo-controlled protocol. It is impossible to mask the individual performing the cryoneurolysis procedure because the ice ball forming at the distal end of the probe—with active treatment—is clearly visible by ultrasound; and the lack of an ice ball for sham participants is equally clear. It is essential to continuously visualize the probe and target nerve throughout the freeze/thaw cycle(s) to ensure the entire nerve diameter is adequately treated and remains relatively motionless. This cannot be achieved if the ultrasound is turned off during nitrous oxide or argon administration to mask the provider; and we prioritize patient safety over masking of the physician administering the intervention. Of note, given that this is a pilot study to help plan for a future trial, unmasking of treatment group assignment may occur following the primary outcome measure exclusively for the Principal Investigator if he feels it will assist in protocol development or requires the data for a future grant proposal.

## **6.4 STUDY INTERVENTION COMPLIANCE**

Not applicable.

## **6.5 CONCOMITANT THERAPY**

Not applicable.

### **6.5.1 RESCUE MEDICINE**

During the procedure we will administer intravenous midazolam and fentanyl. Following the procedure we will not require changes to patients' current medication regimen, and we will not be providing prescriptions for analgesics as well—patients will continue to be under the care of their pre-existing pain physician (or primary care physician).

## **7 STUDY INTERVENTION DISCONTINUATION AND PARTICIPANT DISCONTINUATION/WITHDRAWAL**

### **7.1 DISCONTINUATION OF STUDY INTERVENTION**

Cryoneurolysis procedure will be discontinued if the participant requests during the procedure. Additionally, if the investigator feels that continuing with the intervention would adversely affect the patient's health—such as a hemorrhage—the intervention might be discontinued.

### **7.2 PARTICIPANT DISCONTINUATION/WITHDRAWAL FROM THE STUDY DISCONTINUATION CRITERIA**

1. Patients may withdraw voluntarily from participation in the study at any time and for any reason.
2. Patients may be withdrawn on the basis of the Investigator's clinical judgment, protocol deviation or loss to follow-up.
3. This study may be terminated at the discretion of any regulatory agency for reasons including safety and/or efficacy.
4. The Investigator ([name] and site directors) may elect to discontinue or stop the study at his or her site for any reason including safety.
5. When a participant withdraws or is withdrawn before completing the study, the date and reason for withdrawal are to be documented in the CRF.

6. In the event that a patient is withdrawn prematurely due to an AE or serious AE, the AE or serious AE will be followed until it resolves or stabilizes, or until it is judged by the Site Investigator to be no longer clinically significant.

### 7.3 LOST TO FOLLOW-UP

Study participants may miss data collection phone calls—it is common even though the investigators attempt multiple contacts with participants at specified times—but this study will not consider any patient “lost to follow-up”. We may not be able to collect all data for all participants at all study time points; but we will continue to attempt to contact participants until 12 months has passed for that participant (the duration of study participation) or the participant requests study withdrawal (in which case it is a withdrawal and not “lost to follow-up”).

## 8 STUDY ASSESSMENTS AND PROCEDURES

### 8.1 EFFICACY ASSESSMENTS

**Outcome measurements.** We have selected outcome measures that have established reliability and validity, with minimal inter-rater discordance, and are recommended for chronic pain clinical trials by the Initiative on Methods, Measurement, and Pain Assessment in Clinical Trials (IMMPACT) consensus statement. ***The primary end point will be the difference in average daily phantom pain intensity at baseline and 1 month following the initial intervention (measured with the NRS as part of the Brief Pain Inventory).*** The primary analyses will compare the two treatments (inter-subject comparisons) during the initial treatment period in which half of the subjects will receive active cryoneurolysis and the other half a sham/placebo treatment. Endpoints will be evaluated at baseline and post-treatment (Day 0), Days 1 and 7; and Months 1, 2, 3, 4, and 12, (Table 1). These same time points through month 4 will be evaluated following the optional second (crossover) treatment.

The questionnaire will differentiate among multiple dimensions of limb pain:

***Residual limb (“stump”) pain:*** painful sensations localized to the portion of limb still present.

***Phantom limb sensations:*** non-painful sensations referred to the lost body part.

***Phantom limb pain:*** painful sensations referred to the lost body part.

Each type of pain/sensation will be defined for subjects immediately prior to questionnaire application at each time point, and subjects will be instructed to specifically address phantom limb pain when responding to the various questions. In addition, since there is a strong correlation between phantom and residual limb pain, we will specifically inquire about both types of pain. Each time the questionnaire is applied, subjects will be instructed to respond for the previous 3 days (e.g., worst pain during the previous 3 days) because studies have suggested that patients have “increasing difficulty actually remembering symptom levels beyond the past several days.” Exceptions will be on Day 1 for both the initial and crossover treatments because at these time points, the interest is in subjects’ experiences subsequent to the treatment and not prior to the intervention. During these two days, subjects will be instructed to respond for the period of time since their treatment.

**Table 1. Summary of post-enrollment assessments.**

Subjects:	All							Participating in Crossover *							All
Time Point Following:	Initial Treatment							Crossover Treatment							Initial
Time Point (Days):	0	1	7					0	1	7					
Time Point (Months):				1	2	3	4				1	2	3	4	12
Phantom Limb Pain (worst, least, average, current), NRS	•	•	•	•	•	•	•	•	•	•	•	•	•	•	•
Residual Limb Pain (worst, least, average, current), NRS	•	•	•	•	•	•	•	•	•	•	•	•	•	•	•
Patient Global Impression of Change Scale		•	•	•	•	•	•		•	•	•	•	•	•	•
Brief Pain Inventory Interference Scale	•	•	•	•	•	•	•	•	•	•	•	•	•	•	•
Non-Painful Phantom Sensations (# and duration)	•	•	•	•	•	•	•	•	•	•	•	•	•	•	•
Phantom Limb Pain (# and duration)	•	•	•	•	•	•	•	•	•	•	•	•	•	•	•
Residual Limb Pain (# and duration)	•	•	•	•	•	•	•	•	•	•	•	•	•	•	•

\* The “crossover” treatment intervention will occur 4-6 months following the initial treatment

**Demographic and amputation history.** Subjects will have demographic and anthropomorphic data collected including age, sex, gender, height, weight, years of educational, employment status, marital status, military status, race, ethnicity, current analgesic regimen (including adjuvants such as acupuncture), comorbidities, and any chronic pain other than study limb including location and details. In addition, amputation-specific data will include side of amputation, anatomic location of amputation, contralateral amputation, years since initial amputation, time since phantom pain began, phantom pain description, time since residual pain began, date(s) of subsequent surgical procedures, amputation etiology, amputation level, other amputations (with dates/etiology/pain), and prosthesis use. Immediately prior to premedication the phantom and residual limb pain intensities will be record. Immediately prior to and then following the treatment of each peripheral nerve we will collect the phantom pain score, residual pain score, the treatment point from distal end of limb, duration of argon treatment, and the highest pain during the treatment. We will also note and describe any protocol deviations and adverse events.

All remaining data collection following the day of the intervention (Day 0) will be collected by telephone from the University of California San Diego by the investigators, Program Manager, and/or research coordinators specifically trained in these instruments’ application, minimizing inter-rater discordance

and standardizing responses across all enrolling centers. Staff masked to treatment group assignment will perform all assessments. Each data collection phone call will require approximately 5 minutes.

**Hypothesis 1:** Phantom limb pain **intensity** will be decreased relative to baseline 1 month following a cryoneurolysis procedure (as measured by the Numeric Rating Scale within the Brief Pain Inventory).

Current/present, worst, least, and average phantom pain will be assessed using a Numeric Rating Scale (NRS) as part of the Brief Pain Inventory (short form), with the “average” pain score designated as the primary endpoint. In addition, average and worst residual limb pain NRS will be recorded separately from the phantom pain scores. The NRS is a highly-sensitive measure of pain intensity with numbers ranging from 0 to 10, zero equivalent to no pain and 10 equivalent to the worst imaginable pain. The NRS has been demonstrated to be a valid and reliable measure in multiple pain states—including painful peripheral neuropathy specifically—and following analgesic interventions. In addition, NRS scores correlate well with other measures of pain intensity, and demonstrate high test-retest reliability in chronic nociceptive and neuropathic pain states. These NRS characteristics led to recent IMMPACT consensus recommendations for use of the 10-point NRS of pain intensity for chronic pain trials.

**Hypothesis 2a:** Perception of **well-being** will be improved 1 month following one cryoneurolysis procedure (as measured with the Patient Global Impression of Change Scale).

While single-item measures of pain level/relief are currently the most reliable and valid options to measure pain intensity, the multidimensional aspect of the pain experience has led consensus recommendations for use of “global” measures of improvement in chronic pain trials. The Patient Global Impression of Change Scale is one such measure allowing patient evaluation of integrated treatment effects. This measure is a 7-point ordinal scale requiring the subject to rate the current severity of their global situation as it relates to phantom limb pain (as defined by each individual) compared to their baseline. This scale has the words “very much worse” to the left by the number one, and “very much improved” to the right, adjacent to the number seven. The words “no change” are in the middle of the scale above the number four. The Patient Global Impression of Change Scale has been validated in over ten prospective trials, including studies specifically involving peripheral neuropathy.

**Hypothesis 2b:** Physical and emotional **functioning** will be improved relative to baseline 1 month following one cryoneurolysis procedure (as measured with the Interference Subscale of the Brief Pain Inventory).

It is well-recognized that, “pain is a complex, multidimensional, sensory, and emotional experience that is individually perceived and described in many different ways.” This observation has led to consensus recommendations that “multiple core domains and related measures be considered in pain treatment trials,” that “tap into a wider experience of pain over time and its impact on functioning and quality of life.” Therefore, the proposed trial will include the Brief Pain Inventory, an instrument that includes—in addition to pain intensity scales—seven measures evaluating the pain’s interference with physical and emotional functioning, such as sleep, relations with others, and enjoyment of life. It is this 7-question Interference Scale that will be used specifically for Hypothesis 2b. The Brief Pain Inventory has been used in countless clinical studies of chronic pain, and validated specifically in neuropathic pain states. This instrument is associated with minimal subject burden and is easily interpreted by patients of all ages and education levels. It has high test-retest reliability and correlates well with much longer questionnaires, including the McGill measures and EuroQol.

## 8.2 SAFETY AND OTHER ASSESSMENTS

Prospective subjects will be provided with informed consent and then screened for inclusion and exclusion criteria. The following safety and eligibility procedures will occur during that time:

- **Study Eligibility** – A study investigator will review all medical history, medications and the inclusion/exclusion criteria with the participants.
- **Informed Consent** - Participants will provide written informed consent prior to any other study procedures.
- **Vital Signs** – These include blood pressure, heart rate, temperature and respiratory rate as well as pulse oximetry and continuous 5-lead ECG.
- **Adverse Event Collection** – Patients’ progress notes will be followed during hospitalization and any adverse events recorded. Following discharge, investigators will inquire about any adverse or unexpected events that have occurred since the previous contact. All events will be evaluated by a study investigator and will be followed until resolution.

Any of the safety assessment results will be made available to participants should they request them.

## 8.3 ADVERSE EVENTS AND SERIOUS ADVERSE EVENTS

### 8.3.1 DEFINITION OF ADVERSE EVENTS (AE)

The FDA definition of an Adverse event is any untoward medical occurrence associated with the use of an intervention in humans, whether or not considered intervention-related (21 CFR 312.32 (a)). An AE can be either (a) a new occurrence or (b) an existing process (including the disease under study) that increases significantly in intensity or frequency. The medical product may be a drug or a device, being used either prior to or after regulatory approval.

---

### 8.3.2 DEFINITION OF SERIOUS ADVERSE EVENTS (SAE)

An AE is **serious** when the patient outcome is one or more of the following:

- Death. Applies to the event that is the primary cause of death
- Life-threatening, meaning that the patient was at immediate or substantial risk of death from the event at the time that the event occurred. It does not include an event which hypothetically might have caused death if it occurred in a more severe form.
- Hospitalization, initial or prolonged, meaning that a hospital admission and/or prolongation of a hospital stay was required for the treatment of the AE, or occurred as a consequence of the event. It does not include a pre-planned elective hospital admission for treatment or diagnostic procedures, or, in general, a hospital admission of less than 24 hours duration.
- Disability or incapacity that substantially disrupts the patient's ability to carry out normal life functions and is persistent or significant.
- Congenital anomaly or birth defect.
- Important medical event that, although not immediately life-threatening, requires intervention in order to prevent one of the other serious outcomes listed above. Examples of such events are allergic bronchospasm requiring intensive treatment in an emergency room or at home; blood dyscrasias or convulsions that do not result in hospitalization; or the development of drug dependency or drug abuse.

---

### 8.3.3 CLASSIFICATION OF AN ADVERSE EVENT

---

#### 8.3.3.1 SEVERITY OF EVENT

For adverse events (AEs) not included in the protocol defined grading system, the following guidelines will be used to describe severity.

- **Mild** – Events require minimal or no treatment and do not interfere with the participant's daily activities.
- **Moderate** – Events result in a low level of inconvenience or concern with the therapeutic measures. Moderate events may cause some interference with functioning.
- **Severe** – Events interrupt a participant's usual daily activity and may require systemic drug therapy or other treatment. Severe events are usually potentially life-threatening or incapacitating. Of note, the term "severe" does not necessarily equate to "serious".

---

#### 8.3.3.2 RELATIONSHIP TO STUDY INTERVENTION

All adverse events (AEs) must have their relationship to study intervention assessed by the clinician who examines and evaluates the participant based on temporal relationship and his/her clinical judgment.

The degree of certainty about causality will be graded using the categories below. In a clinical trial, the study product must always be suspect.

- **Related** – The AE is known to occur with the study intervention, there is a reasonable possibility that the study intervention caused the AE, or there is a temporal relationship between the study intervention and event. Reasonable possibility means that there is evidence to suggest a causal relationship between the study intervention and the AE.
- **Not Related** – There is not a reasonable possibility that the administration of the study intervention caused the event, there is no temporal relationship between the study intervention and event onset, or an alternate etiology has been established.

---

#### 8.3.3.3 EXPECTEDNESS

[name], study Principal Investigator (PI) will be responsible for determining whether an adverse event (AE) is expected or unexpected. An AE will be considered unexpected if the nature, severity, or frequency of the event is not consistent with the risk information previously described in the risk section for the study intervention.

---

### 8.3.4 TIME PERIOD AND FREQUENCY FOR EVENT ASSESSMENT AND FOLLOW-UP

The occurrence of an adverse event (AE) or serious adverse event (SAE) may come to the attention of study personnel during hospitalization or post-discharge follow-up data-collection phone calls.

All AEs including local and systemic reactions not meeting the criteria for SAEs will be captured on the appropriate case report form (CRF). Information to be collected includes event description, time of onset, clinician's assessment of severity, relationship to study product (assessed only by those with the training and authority to make a diagnosis), and time of resolution/stabilization of the event. All AEs occurring while on study must be documented appropriately regardless of relationship. All AEs will be followed to adequate resolution.

Any medical condition that is present at the time that the participant is screened will be considered as baseline and not reported as an AE. However, if the study participant's condition deteriorates at any time during the study, it will be recorded as an AE.

Changes in the severity of an AE will be documented to allow an assessment of the duration of the event at each level of severity to be performed. AEs characterized as intermittent require documentation of onset and duration of each episode.

A study coordinator will record all reportable events with start dates occurring any time after informed consent is obtained until 7 (for non-serious AEs) or 30 days (for SAEs) after the last day of study participation. At each study visit, the investigator will inquire about the occurrence of AE/SAEs since the last visit. Events will be followed for outcome information until resolution or stabilization.

***Precautions and responses to possible specific adverse events:***

**Infection:** Cryoneurolysis will be placed under sterile conditions as is standard-of-care. In addition, all patients having mastectomy will receive perioperative antibiotics, which will further decrease any risk of infection. Should a treatment site become infected, the patient will have oral antibiotics prescribed.

**Bleeding:** Exclusion criteria include ongoing active anticoagulation and/or bleeding disorders to decrease the risk of bleeding. During application, vessels are avoided with the use of real-time ultrasound guidance. The investigators are all specifically trained and have experience using ultrasound guidance.

**Skin discoloration:** Discoloration only occurs if the ice ball encompasses the dermis and epidermis. For the current study, the target nerves will be 2-10 cm in depth with the ice ball radius approximately 0.5-1.0 cm (depending on thickness of treated nerve), so the ice ball will not be close to the epidermis. Using ultrasound guidance, the skin, muscles, and target nerves are easily imaged in real-time and avoiding the epidermis is a basic maneuver.

**Confidentiality:** The risks to confidentiality are the release of names/ telephone numbers/ demographic data (e.g. weight, age, height), which will be minimized by the use of password-protected computers and case report forms that will be stored in locked offices.

---

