Residual Limb Pain (# and duration)	•	•	•	•	•	•	•	•	•	•	•	•	•	•	•	•																																																																																																																																																																														
Study Population	There will be approximately 25 participants.																																																																																																																																																																																													
	Inclusion criteria:																																																																																																																																																																																													

	
(1) Adult patients of at least 18 years of age
 
(2) Trans-femoral traumatic or surgical amputation at least 12 weeks prior to enrollment distal to the hip (femoral head remaining)
 
(3) Experiencing at least moderate phantom limb pain—defined as a 4 or higher on the Numeric Rating Scale (NRS; 0-10, 0= no pain; 10=worst imaginable pain)—at least daily for the previous 2 months
 
(4) willing to avoid both changes to their analgesic regimen as well as elective surgical procedures from 1 month prior to and at least 4 months following the initial cryoneurolysis procedure.
 
Exclusion criteria:
 
(1) allergy to amide local anesthetics
 
(2) pregnancy
 
(3) incarceration
 
(4) inability to communicate with the investigators
 
(5) morbid obesity (body mass index > 40 kg/m^2)
 
(6) possessing any contraindication specific to cryoneurolysis such as a localized infection at the treatment site, cryoglobulinemia, cold urticaria and Reynaud's Syndrome

Phase:	Not applicable to this investigation involving a medical device (as opposed to a medication)
Description of Sites/ Facilities Enrolling Participants	U.C. San Diego Clinical and Translational Research Institute

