## 1.2 SCHEMA

## 1.3 SCHEDULE OF ACTIVITIES (SOA)

Subjects:	All							Participating in Crossover *							All
Time Point Following:	Initial Treatment							Crossover Treatment							Initial
Time Point (Days):	0	1	7					0	1	7					
Time Point (Months):				1	2	3	4				1	2	3	4	12
Written Informed Consent	•														
Screening for eligibility	•														
Urine Pregnancy test ( as needed)	•							•							
Randomization	•														
Conscious sedation and study treatment	•							•							
Phantom Limb Pain (worst, least, average, current), NRS	•	•	•	•	•	•	•	•	•	•	•	•	•	•	•
Residual Limb Pain (worst, least, average, current), NRS	•	•	•	•	•	•	•	•	•	•	•	•	•	•	•
Patient Global Impression of Change Scale		•	•	•	•	•	•	•	•	•	•	•	•	•	•
Brief Pain Inventory Interference Scale	•	•	•	•	•	•	•	•	•	•	•	•	•	•	•
Non-Painful Phantom Sensations (# and duration)	•	•	•	•	•	•	•	•	•	•	•	•	•	•	•
Phantom Limb Pain (# and duration)	•	•	•	•	•	•	•	•	•	•	•	•	•	•	•
Residual Limb Pain (# and duration)	•	•	•	•	•	•	•	•	•	•	•	•	•	•	•

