### 5.2 EXCLUSION CRITERIA

- (1) allergy to amide local anesthetics
- (2) pregnancy
- (3) incarceration
- (4) inability to communicate with the investigators
- (5) morbid obesity (body mass index > 40 kg/m^2)
- (6) possessing any contraindication specific to cryoneurolysis such as a localized infection at the treatment site, cryoglobulinemia, cold urticaria and Reynaud's syndrome

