**Optional crossover treatment.** Four to six months following the initial treatment, subjects *may* return for an optional repeated intervention procedure (“crossover”) with the alternative treatment (either active cryoneurolysis or sham/placebo), again in a double-masked fashion using the same protocol as described for the initial intervention. **The crossover treatment is not required for study participation, as the primary analyses will include a parallel study design for the initial intervention evaluated prior to any crossover treatment.** However, an optional crossover treatment will be offered to subjects for two reasons: (1) it will ensure that all subjects have access to the proposed treatment, regardless of the treatment they are initially randomized to; and (2) it will permit intra-subject differences between treatments to be analyzed (e.g., assessing treatment-effect heterogeneity, or the variability of the causal effect across individuals, which will would not be available from the parallel-group portion of the study alone). These intra-subject differences will be secondary analyses, as there may be patient-selection bias regarding which subjects decide to have the crossover treatment (e.g., if the intervention is successful at greatly reducing phantom limb pain, then subjects receiving active cryoneurolysis during their initial treatment will be more likely to forgo the crossover treatment). This crossover will *not* affect the primary analyses, which will involve a parallel group study design and investigate the effects of cryoneurolysis within 4 months of the initial intervention. The approximate duration of a crossover visit will total 4 hours, from the time the subject enters the treatment facility until the time the depart. Following study completion, the results will be provided to all enrolled subjects using non-technical (i.e. “layperson”) language, along with their treatment group assignment at the participants’ request.

Following study completion, the results will be mailed electronically or by the United States Postal Service to all enrolled participants in written form using non-technical (e.g., “layperson”) language.

---

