1. Identifiers will include the potential participant's age, level of amputation, pain levels, and willingness to avoid both changes to their analgesic regimen as well as elective surgical procedures from 1 month prior to and at least 4 months following the initial cryoneurolysis procedure. In addition, we will inquire about any allergy to amide local anesthetics, pregnancy, incarceration, ability to read English (for the ICF), weight and contraindications specific to cryoneurolysis such as a localized infection at the treatment site or Reynaud's syndrome. This information will not need to be recorded in hard-copy format. If the patient does not participate, then there will be no record of PHI specifically for study

purposes whatsoever. If the patient does participate, then PHI will be recollected following written, informed consent.

2. This clinical trial could not be practicably carried out without the waiver because we must ascertain inclusion/exclusion criteria before the prospective patient has travelled to the medical center. If they meet criteria, then they can decide whether or not to schedule the intervention; and we will collect written, informed consent as documented with an IRB-approved ICF at the beginning of their visit and prior to any questionnaires or procedures.

3. The privacy risk to individuals whose PHI will be used is minimal since we will not record any PHI specifically for study purposes until after written, informed consent is provided. The anticipated benefit to participants is a chance of improving their pain control if they are randomized to active treatment.

4. PHI that will be evaluated includes the items listed in #1 above.

An investigator or research coordinator will review the study protocol in detail with interested prospective participants; and, for patients desiring participation, written, informed consent will be obtained prior to any measurements, data collection, and/or interventions. The method of documenting informed, written consent will be IRB-approved consent forms. Vulnerable populations will not be enrolled.

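### Section 8.3.4 relies on an exclusion for anticoagulation and bleeding disorders that no eligibility or screening list contains

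*Combined protocol and SAP*

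**What the plan says.** Among the precautions for specific adverse events, Section 8.3.4 gives this for bleeding: "Exclusion criteria include ongoing active anticoagulation and/or bleeding disorders to decrease the risk of bleeding". The same paragraph adds that vessels are avoided under real-time ultrasound.

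The synopsis and Section 5.2 each list six exclusions: allergy to amide local anesthetics, pregnancy, incarceration, inability to communicate with the investigators, body mass index above 40, and a final open-ended item, which in Section 5.2 reads "possessing any contraindication specific to cryoneurolysis such as a localized infection at the treatment site, cryoglobulinemia, cold urticaria and Reynaud's syndrome".

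Section 10.1.1 lists what candidates are asked before they travel. Its last item is "contraindications specific to cryoneurolysis such as a localized infection at the treatment site or Reynaud's syndrome".

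Section 8.2 describes the eligibility review: "A study investigator will review all medical history, medications and the inclusion/exclusion criteria with the participants". The baseline data list in Section 8.1 includes "current analgesic regimen (including adjuvants such as acupuncture), comorbidities".

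The schedule in Section 1.3 marks "Screening for eligibility" at initial Day 0 only. It marks the urine pregnancy test at Day 0 of both the initial and the crossover treatment. Under Section 6.1.1 the optional crossover takes place four to six months after the first treatment, "again in a double-masked fashion using the same protocol as described for the initial intervention".

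**The concern.** The safety section presents the exclusion as already in force. An ethics board reading Section 8.3.4 would take it that people on anticoagulants or with bleeding disorders cannot enter. Staff working from Section 5.2 would find no such rule. Both statements are current text, and the amendment history records no change to eligibility that would explain the difference.

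At stake is one bleeding precaution, for the candidates who have these conditions. It is the only precaution in that paragraph that acts before a probe is inserted. Probes go to the femoral, sciatic, obturator and lateral femoral cutaneous nerves, and Section 8.3.4 puts the target nerves at 2-10 cm depth. Sham participants have a probe inserted as well; it is simply not activated. The exposure therefore exists in both arms.

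**Working it through.** The main check compares texts. The plan gives no figure to reproduce.

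**1. Is the exclusion in any list?**

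| Place | Anticoagulation or bleeding disorder named? |
|---|---|
| Section 8.3.4, bleeding precaution | Yes, described as an existing exclusion |
| Section 1.1, six exclusions | No |
| Section 5.2, six exclusions | No |
| Section 5.1, inclusion criteria | No |
| Section 10.1.1, pre-screening items | No |
| Section 1.3, schedule | No; a general eligibility screen and a pregnancy test only |

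The rule is in 0 of the 2 exclusion lists and not among the pre-screening items.

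**2. Does the sixth exclusion cover it?** That item is open-ended but limited to contraindications specific to cryoneurolysis. Its examples are a local infection and cold-related conditions. Bleeding risk comes with any percutaneous probe. An investigator could stretch the item to cover it, but nothing in the lists says to.

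**3. Does the visit review cover it?** The Section 8.2 review takes in history and medications, so an anticoagulant may come to light. The criteria it is compared with contain no coagulation rule. In the Section 8.1 baseline list the only medication item is the analgesic regimen; comorbidities are recorded too.

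**4. What about the crossover?** Eligibility screening is marked once. The procedure is repeated 4-6 months later, so an anticoagulant started in between meets no scheduled eligibility check. Each session treats 4 nerves, so a participant who takes the crossover has 4 + 4 = 8 nerve sites entered over the two sessions.

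**5. How many participants might this involve?** The documents do not give the share p of otherwise eligible candidates with these conditions. The values below are assumptions. They also assume that the Section 8.2 review turns none of them away, so for each p the result is an upper bound. With n = 25, the expected number enrolled is n × p, and the chance of at least one is 1 − (1 − p)^n.

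| Assumed p | Expected number, 25 × p | Chance of at least one, 1 − (1 − p)^25 |
|---|---|---|
| 2% | 0.5 | 0.397 |
| 5% | 1.25 | 0.723 |
| 10% | 2.5 | 0.928 |
| 20% | 5 | 0.996 |

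These are chances of enrollment, not of harm. The documents give no bleeding rate from which harm could be derived.

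**The case against.** The strongest case on the other side accepts the mismatch and disputes its weight.

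- **The sixth exclusion is open-ended.** Its first example, infection at the treatment site, is as general to percutaneous procedures as bleeding is. Read together with Section 8.3.4, the item could take in anticoagulation. This shows the item is ambiguous. It does not supply a rule that all staff would apply alike.
- **The rule is written down and an investigator sees the medications.** Section 8.3.4 is part of the same protocol, and Section 7.2 allows withdrawal on clinical judgment. These make enrollment less likely. They still leave exclusion to individual judgment, and Section 10.1.7 provides no formal monitoring to catch an omission.
- **Section 10.1.1 is weak evidence.** It supports a privacy waiver, does not match Section 5.2 exactly, and the eligibility form itself is not in the documents. This is fair. The conclusion rests mainly on the synopsis and Section 5.2.
- **The prevalence figures restate an assumption.** This is also fair, and the finding does not depend on them.
- **The crossover point is general.** Of the listed exclusions only pregnancy is marked for recheck, and staff ask about new events at each contact. Such questions may reveal a new anticoagulant, but they are not an eligibility check.
- **The sentence may be left over from another protocol.** The preceding infection paragraph mentions mastectomy patients, so this is plausible. In that case the safety section claims a safeguard that was never meant, which also needs correcting.
- **The stake is small.** The very-low-risk statement in Section 2.3.1 rests on probe design and gives holding pressure as the response. Ultrasound guidance and stopping for hemorrhage (Section 7.1) remain. This stands, and it limits the severity.

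**Conclusion.** The concern holds. Section 8.3.4 states an exclusion that the eligibility lists do not contain, and a person on anticoagulants or with a bleeding disorder can meet every listed criterion. This is more than a wording slip, because it changes who may be treated. It should be fixed.

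Its reach is limited: one bleeding precaution, only for candidates with these conditions, among at most 25 participants, with other precautions still in place. The primary endpoint and its analysis are untouched. The conclusion rests on the text alone and needs no assumption about prevalence. Which of the two statements the investigators intended cannot be settled from the documents.

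**What to change.** If the exclusion is intended, add ongoing active anticoagulation and/or a bleeding disorder to the exclusions in Sections 1.1 and 5.2 and to the pre-screening items in Section 10.1.1. Add a recheck at crossover Day 0 in the Section 1.3 schedule, as is already done for the pregnancy test.

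If it is not intended, delete the sentence in Section 8.3.4 and state how anticoagulated participants will be managed.

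In either case, remove the mastectomy antibiotic sentence from Section 8.3.4 in the same amendment.

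Keeping the exclusion costs one line in each of three lists and one schedule mark. It may also shrink the eligible pool, by an amount the documents do not give.
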